1. PURPOSE OF THE STUDY

a. Brief Summary

The purpose of the LEAPS program is to understand how a trained lay health worker who engages with newly diagnosed patients after a diagnosis of an advanced stage of cancer can help to improve patient satisfaction with their decision-making, activation, quality of life, and healthcare resource utilization.

b. Objectives

We hope to better understand how to help improve patients' care after a diagnosis of advanced cancer. We want to better understand the influence of a local lay health coach on improving patient's efficacy, quality of life, and satisfaction. We also want to know the impact of the program on healthcare resource utilization (emergency department, hospitalization, hospice utilization).

c. Rationale for Research in Humans

Because this is a novel program focused on helping patients better understand their goals of care, human subjects must be used for this project.

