2. STUDY PROCEDURES

a. Procedures

Unite Here Health will institute a novel program focused on providing patients with a lay health coach who will engage patients with goals of care after a diagnosis of cancer. Unite Here Health will enroll patients into the study after a new diagnosis of cancer or after a diagnosis of cancer that has progressed to a worsening stage. Unite Here Health staff will identify patients for the program through primary care physicians, oncologist referrals, and hospitalization daily notice of admissions and emergency department reports which Unite Here Health routinely receives as part of usual care. Patients without capacity to consent verbally will not be eligible for the study.

The Unite Here Health staff will contact eligible patients by telephone to introduce the study. If the patient is interested, he/she will be randomized into the usual oncology care arm versus the lay health worker intervention arm. Patients randomized into the intervention will be assigned a lay health worker who will contact the patient to begin the intervention. The intervention includes: education on early advance care planning,

documenting goals of care, assessing symptoms, and coordinating community services (such as home health, home visits, and home hospice).

The Unite Here Health staff, as part of their usual assessments, will conduct the following assessments for patients enrolled in the intervention and the usual oncology care arm at time of randomization and at 6 and 12 months after enrollment: a satisfaction with decision-making survey to compare changes in satisfaction, a patient activation measure survey (PAM survey), and the Functional Assessment of Cancer Therapy - General quality of life survey. At these time points, additional data collected as part of usual care will also be assessed for each patient. This includes: healthcare utilization (total number of emergency department visits and hospitalizations, referral to palliative care, and hospice receipt). This data will be abstracted from the patients' claims data that Unite Here Health routinely reviews and collects.

b. Procedure Risks

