The risks to subjects will be minimized as this is a study that provides usual oncology care. As part of the study intervention, additional support services will be provided to patients. Usual care procedures at the local site ensure sound procedures to minimize data sharing risk. There are no identifiers that will be collected or shared with the Stanford PI.

c. Use of Deception in the Study

No deception will be used.

d. Use of Audio and Video Recordings

No recordings will occur.

e. Alternative Procedures or Courses of Treatment

The study could improve documentation of patients' overall goals of care and could lead to a reduction in unwanted healthcare utilization. No standard of treatment will be withheld from patients. There are no potential risks to the patients involved in the study other than breach of confidentiality however no identifiers will be collected or shared with Stanford PI in the analysis of the data.

f. Will it be possible to continue the more (most) appropriate therapy for the participant(s) after the conclusion of the study?

Yes

g. Study Endpoint(s)

The primary endpoint is the Edmonton Symptom Assessment System (ESAS) at 12 months.

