6. BENEFITS

The benefit from this study will help to inform whether a lay health coach can improve patient satisfaction, quality of life, and reduce healthcare utilization for patients diagnosed with advanced cancer.

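### The primary endpoint in section 2g (ESAS at 12 months) measures symptom burden, which none of the protocol's statements of its question mentions

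*Protocol*

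**What the plan says.** The protocol states its question in four places.

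- Section 1a: whether a lay health worker "can help to improve patient satisfaction with their decision-making, activation, quality of life, and healthcare resource utilization".
- Section 1b: "We want to better understand the influence of a local lay health coach on improving patient's efficacy, quality of life, and satisfaction", followed by a sentence on emergency department, hospital and hospice use.
- Section 3a: after an earlier trial in a VA system, it is unclear whether such a program improves quality of life and satisfaction and lowers utilization elsewhere.
- Section 6: the expected benefit is evidence on "whether a lay health coach can improve patient satisfaction, quality of life, and reduce healthcare utilization for patients diagnosed with advanced cancer".

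Section 2g, on study endpoints, holds one sentence: "The primary endpoint is the Edmonton Symptom Assessment System (ESAS) at 12 months". It lists no other endpoint, primary or secondary.

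Section 2a sets the assessments for both arms at randomization, 6 and 12 months: a decision-satisfaction survey, the PAM, "the Functional Assessment of Cancer Therapy - General quality of life survey", and utilization from claims. ESAS is not on that list, nor among the three surveys in section 5a.

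**The concern.** The primary endpoint carries the trial's main conclusion, so it should measure something the objectives ask about. Here the objectives and the primary endpoint are both fixed in the same document, and they point at different things.

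Two results show what is at stake. Suppose ESAS favours the intervention while satisfaction, FACT-G and utilization do not differ. The trial is then positive on its primary endpoint, yet nothing in section 6 has been shown. Suppose instead that satisfaction and FACT-G improve and ESAS does not. The trial then fails on its primary endpoint, although much of its stated purpose has been met. In both cases the headline result and the stated question come apart.

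**Working it through.** There is no figure in the plan to reproduce. The check is a comparison of texts.

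**Step 1. Outcome domains in each statement of the question.**

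| Section | Domains named | Number | Symptom burden or ESAS |
|---|---|---|---|
| 1a Brief Summary | decision satisfaction, activation, quality of life, utilization | 4 | 0 of 4 |
| 1b Objectives | efficacy, quality of life, satisfaction, utilization | 4 | 0 of 4 |
| 3a Background | quality of life, satisfaction, utilization | 3 | 0 of 3 |
| 6 Benefits | satisfaction, quality of life, utilization | 3 | 0 of 3 |

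Activation or efficacy appears only in 1a and 1b. The other three domains appear in all four.

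**Step 2. Which instrument serves each domain.** Section 2a supplies a decision-satisfaction survey for satisfaction, the PAM for activation, FACT-G for quality of life and claims data for utilization. Efficacy in 1b has no instrument named for it; I assume the PAM is meant. No domain is left for ESAS to serve.

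**Step 3. Whether ESAS could count as the quality-of-life measure.** Quality of life is the closest domain, but 2a assigns it to FACT-G, and 5a again lists a quality-of-life assessment among the three surveys. The protocol treats it as separate from ESAS.

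**Step 4. Where symptoms appear elsewhere.** In 2a and 5a, symptom assessment is part of what the lay health worker does. In Appendix 1, ESAS is the worker's telephone screening tool, and symptom relief is given as the purpose when the worker introduces the program to the patient. That appendix is titled as a symptom-assessment quality improvement pilot. These texts describe the intervention. None states a study objective.

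**Step 5. Measures labelled as endpoints.** One, ESAS at 12 months (2g). Of the domains in step 1, it matches none.

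**Step 6. Whether scheduling ESAS would be enough.** No. If ESAS were collected completely in both arms, the primary test would still concern a domain absent from 1a, 1b, 3a and 6. The missing schedule is a separate gap, but it bears on the remedy, since an ESAS primary endpoint cannot be analysed without it.

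**The case against.** The best defence has two parts. First, symptoms are not foreign to this program: symptom assessment is an intervention component in 2a, and Appendix 1 presents symptom relief as the program's aim when it is introduced to patients. Second, the outcomes in the objectives have named measures, collection in both arms and fixed times in 2a. They lack only the label of endpoint, and a statistical analysis plan could rank them.

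Much of this stands. ESAS is a plausible outcome for such an intervention, and the 2a data can inform the objectives. It does not remove the mismatch. An intervention component is not an objective, and an analysis plan that ranks secondary outcomes would not make ESAS answer sections 1, 3a and 6.

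A reader might infer three stronger points, which the document does not support.

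- **That false-positive risk is uncontrolled across the outcomes in 2a.** The protocol states no significance level and no plan to test each outcome. Multiplicity control and testing order commonly sit in an analysis plan, which is not shown. That risk would also be unchanged if symptom burden were written into section 1, so it does not measure this problem.
- **That the aim of lower utilization in section 6 clashes with counting hospice and palliative referral in 2a.** Section 2a lists the items separately and forms no composite, 1b asks neutrally about impact, and 2e speaks of reducing only unwanted use. No passage states that hospice use or palliative referral is meant to rise.
- **That an ESAS result would say nothing about the program.** It would say something about symptoms, which the program addresses. It would not answer the question the protocol puts.

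**Conclusion.** The point holds as an inconsistency within the protocol. The primary endpoint in 2g belongs to none of the domains in 1a, 1b, 3a or 6, and the nearest domain, quality of life, has its own instrument. The primary test as written does not address the stated question.

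The size is the count in step 1: zero of four statements name symptom burden. No error rate or power loss can be attached. The protocol gives no significance level, power, effect size or standard deviation, and supports its sample size of 180 by feasibility alone.

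The conclusion assumes that sections 1, 3a and 6 state the intended question, and that 2g means ESAS as a measure of symptom burden. It does not extend to saying that the trial cannot inform its objectives. The change should be made, but it is a matter of alignment and does not require a different design.

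**What to change.** Before outcomes are compared by arm, reconcile 2g with 1a, 1b and 6 in one of two ways.

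**(a) Keep ESAS primary.** State symptom burden as the primary objective in 1a and 1b. Add ESAS to the both-arm assessments in 2a and 5a at baseline, 6 and 12 months. Word section 6 so that claims on satisfaction, quality of life and utilization are secondary. The cost is one more short survey in both arms.

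**(b) Change the primary endpoint.** In 2g, make primary a measure that matches the stated objectives and is already collected in both arms under 2a, for example FACT-G or satisfaction with decision at 12 months, and make ESAS secondary. The cost is a changed primary endpoint, to be dated and explained in an amendment. The protocol contains no power calculation that this would upset; if the analysis plan has one for ESAS, it would need redoing. Any comparison of ESAS between arms as a secondary outcome would still need ESAS collected in usual care.

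Either route is sound. The choice depends on which question the sponsor means to answer, and the document does not settle that. The order of the remaining outcomes can be left to the analysis plan.

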2. STUDY PROCEDURES

a. Procedures

Unite Here Health will institute a novel program focused on providing patients with a lay health coach who will engage patients with goals of care after a diagnosis of cancer. Unite Here Health will enroll patients into the study after a new diagnosis of cancer or after a diagnosis of cancer that has progressed to a worsening stage. Unite Here Health staff will identify patients for the program through primary care physicians, oncologist referrals, and hospitalization daily notice of admissions and emergency department reports which Unite Here Health routinely receives as part of usual care. Patients without capacity to consent verbally will not be eligible for the study.

The Unite Here Health staff will contact eligible patients by telephone to introduce the study. If the patient is interested, he/she will be randomized into the usual oncology care arm versus the lay health worker intervention arm. Patients randomized into the intervention will be assigned a lay health worker who will contact the patient to begin the intervention. The intervention includes: education on early advance care planning,

documenting goals of care, assessing symptoms, and coordinating community services (such as home health, home visits, and home hospice).

The Unite Here Health staff, as part of their usual assessments, will conduct the following assessments for patients enrolled in the intervention and the usual oncology care arm at time of randomization and at 6 and 12 months after enrollment: a satisfaction with decision-making survey to compare changes in satisfaction, a patient activation measure survey (PAM survey), and the Functional Assessment of Cancer Therapy - General quality of life survey. At these time points, additional data collected as part of usual care will also be assessed for each patient. This includes: healthcare utilization (total number of emergency department visits and hospitalizations, referral to palliative care, and hospice receipt). This data will be abstracted from the patients' claims data that Unite Here Health routinely reviews and collects.

b. Procedure Risks

The risks to subjects will be minimized as this is a study that provides usual oncology care. As part of the study intervention, additional support services will be provided to patients. Usual care procedures at the local site ensure sound procedures to minimize data sharing risk. There are no identifiers that will be collected or shared with the Stanford PI.

c. Use of Deception in the Study

No deception will be used.

d. Use of Audio and Video Recordings

No recordings will occur.

e. Alternative Procedures or Courses of Treatment

The study could improve documentation of patients' overall goals of care and could lead to a reduction in unwanted healthcare utilization. No standard of treatment will be withheld from patients. There are no potential risks to the patients involved in the study other than breach of confidentiality however no identifiers will be collected or shared with Stanford PI in the analysis of the data.

f. Will it be possible to continue the more (most) appropriate therapy for the participant(s) after the conclusion of the study?

Yes

g. Study Endpoint(s)

The primary endpoint is the Edmonton Symptom Assessment System (ESAS) at 12 months.

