4. PARTICIPANT POPULATION

a. Planned Enrollment

At the local site, Unite Here Health will enroll a total of 180 patients into the study. Inclusion criteria are as follows:

1. Newly diagnosed patients with a cancer diagnosis.
2. Patients with any relapse or progressive disease (any cancer diagnosis) as identified by imaging or biopsy and confirmed by physician.
3. The patients must be 18 years or older.
4. Patients must have the capacity to verbally consent.

The total number of patients with cancer who are members of Unite Here Health are 200 per year. Therefore we anticipate that we will feasibly be able to enroll 180 patients into the study during the first 18 months.

b. Age, Gender, and Ethnic Background

The age range is > 18, gender is both male and female, and ethnic population is Hispanic, Asian/Pacific Islander, Non-Hispanic White, Non-Hispanic Black, American Indian, and Alaskan Native.

c. Vulnerable Populations

We will not enroll children or pregnant women. The study will be offered to all patients regardless of economic status. Patients who are unable to consent to participation will not be included.

d. Rationale for Exclusion of Certain Populations

Children are not included because the study is focused on adult patients with cancer. Additionally, Unite Here Health does not have any members less than the age of 18.

e. Recruitment Details

All eligible patients at Unite Here Health will be identified and referred into the study by the primary oncologist, primary care physician, or through daily inpatient and emergency

department reports which are routinely sent to the Unite Here Health staff as part of usual care.

f. Eligibility Criteria

i. Inclusion Criteria

1. Newly diagnosed patients with a cancer diagnosis.
2. Patients with any relapse or progressive disease (any cancer diagnosis) as identified by imaging or biopsy and confirmed by physician.
3. The patients must be 18 years or older.
4. Patients must have the capacity to verbally consent.

ii. Exclusion Criteria

Inability to consent to the study due to lack of capacity as documented by the referring physician.

Patients without a newly diagnosed malignancy or patients without relapse of disease.

g. Screening Procedures

There are no screening procedures for enrollment in the study.

h. Participation in Multiple Protocols

There are no other studies ongoing at Unite Here Health that may lead to dual enrollment in studies.

i. Payments to Participants

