5. RISKS

a. Potential Risks

As part of the study, patients will receive either usual care or will be assigned into the intervention. Patients assigned to the intervention will receive a lay health coach assigned to educate patients in goals of care, assist with symptom assessments, and coordinate community care (such as home hospice, home health services). All patients in the study will receive 3 surveys at baseline, 6 and 12 months after study enrollment: satisfaction with decision, patient activation, and quality of life assessment. receive satisfaction

surveys with their care (CAPHS-G). These will be anonymous surveys and will not be linked to the patient.

b. Procedures to Minimize Risk

We will not obtain identifiable records. For analysis purposes, all patients enrolled into the study will be assigned a unique identifier number. Data will be provided to the Stanford PI in aggregate. Patients will be coded and no direct identifiers will be linked to the patient. All data will be kept in a secure REDCAP database without any patient identifiers other than a unique identifier code.

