Appendix 1: Patient Procedures

Stanford –CareMore-Oncology Institute of Hope and Innovation- Lay Health Worker Symptom Assessment Quality Improvement Pilot

Identifying Patients

- ❖ All patients with newly diagnosed cancer Stage 3 or 4 or hematologic malignancies requiring Medical Oncology will be included in the program.
- 1) Patients will be categorized as either "High Risk" or "Low-Risk" based on the following criteria:
- 1) High Risk: All metastatic cancer patients as well as all patients on active chemotherapy, all patients with symptom scores 4 or above, or any change in symptom of greater than 2 points from prior assessment
- 2) Low Risk: Patients who are not on chemotherapy and are undergoing routine follow-up/surveillance, who have no symptom scores of 4 or above, and no change in symptom scores
- 3) Three months after a non-metastatic patient has completed adjuvant chemotherapy or treatment, he/she will be transitioned to low-risk status unless trigger event occurs as above.

Patient Engagement

- LHW will contact all patients via telephone who meet the criteria prior to their first oncology appointment
- LHW will schedule an initial oncology consultation appointment with the patient within 5 days of initial contact
- LHW will discuss program
- LHW will prepare the patient for their upcoming initial consultation with an oncologist
- LHW will invite and encourage the patient to include anyone in the conversation such as family/caregiver and encourage the patient to include anyone who may potentially be attending future oncology appointments with the patient.
 - If necessary, the LHW will offer to reschedule the call to accommodate patient's request for others to be present during conversation.
- LHW will provide contact information for patients to use in the event of any future triggers and provide a list of all the appropriate triggers to the patient and the care circle.
 - Triggers Include:
 - Disease progression
 - Unexpected side effects
 - Potential change of treatment
 - ED visit or hospital use
 - If for any reason patient does not feel comfortable
 - Life situation changes in a manner that potentially impacts symptoms
 - Oncologist refers patient back to the LHW
 - Patient family members need education/clarification/support

Introduction of HVCCP

- ❖ Explain the purpose is to help patients maintain symptom relief.
 - The LHW is here to support the patient throughout this process

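### Section 2a words the satisfaction comparison as one of changes; follow-up scores adjusted for the score at randomization would be at least as precise and usually more so, provided the surveys can be linked within patient.

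*Protocol*

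**What the plan says.** Protocol section 2a lists three surveys for both arms: satisfaction with decision-making, patient activation (PAM) and FACT-G quality of life. They are given "at time of randomization and at 6 and 12 months after enrollment". Only the first has a comparison attached to it: "a satisfaction with decision-making survey to compare changes in satisfaction". No estimator, model, covariate or time point follows.

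Other places bear on the point:

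- **Entry.** Section 2a enrolls patients "after a new diagnosis of cancer or after a diagnosis of cancer that has progressed to a worsening stage". Section 4f admits both new diagnoses and relapse or progression.
- **Timing of first contact.** Appendix 1 states that "LHW will contact all patients via telephone who meet the criteria prior to their first oncology appointment". That appendix is headed as a differently named quality-improvement pilot.
- **Status of the outcome.** Section 1a names satisfaction with decision-making among the aims. Section 2g, however, says: "The primary endpoint is the Edmonton Symptom Assessment System (ESAS) at 12 months".
- **Size.** "Unite Here Health will enroll a total of 180 patients into the study" (section 4a). The number rests on feasibility, and no power calculation is given.
- **Linkage.** Section 5a says of surveys: "These will be anonymous surveys and will not be linked to the patient". Section 5b gives every patient a study code, but also says that the academic investigator receives data in aggregate.

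**The concern.** An analyst told to compare changes would ordinarily subtract the baseline from the follow-up score and compare the differences between arms. Subtraction gives the baseline a fixed weight of one, whatever its relation to the follow-up score. Covariate adjustment estimates that weight from the data. Both estimate the same treatment effect in a randomized trial, so the issue is variance and not bias.

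Subtraction does worst when baseline and follow-up are weakly correlated, and this survey could be such a case. A newly diagnosed patient surveyed at randomization might not yet have made a treatment decision, and a patient with relapse might be rating decisions about earlier disease. The later surveys would rate later decisions, so the difference would be noisy and hard to interpret. A patient with nothing to rate at baseline would also have no change score and would drop out of a change analysis.

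**Working it through.** **Inputs.** The documents supply the assessment times (section 2a) and the total of 180 (section 4a). They state no correlation, SD, effect size, alpha, power, dropout or allocation ratio, so there is no figure of the plan's own to reproduce. Assumed for illustration: 1:1 allocation (90 per arm), two-sided 0.05, a difference of 0.4 SD, and a range of r.

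**Step 1: general variances.** Let SD0 be the baseline SD, SD1 the follow-up SD and r their correlation. Per patient:

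- change score: SD0² + SD1² − 2·r·SD0·SD1
- follow-up alone: SD1²
- follow-up adjusted for baseline: SD1²·(1 − r²)

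Change minus adjusted is SD0² − 2·r·SD0·SD1 + r²·SD1² = (SD0 − r·SD1)². A square cannot be negative, so in large samples adjustment is never less precise. The two tie only when SD0 = r·SD1. For example, with SD0 = 0.5, SD1 = 1 and r = 0.5, change gives 0.25 + 1 − 0.5 = 0.75 and adjustment gives 1 − 0.25 = 0.75.

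**Step 2: equal SDs.** With SD0 = SD1 = 1 the variances are 2(1 − r), 1 and 1 − r². The adjusted-to-change ratio is (1 − r²)/(2(1 − r)) = (1 + r)/2. Change is noisier than ignoring baseline when 2(1 − r) > 1, that is, r < 0.5. With unequal SDs that threshold becomes SD0/(2·SD1).

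**Step 3: numbers.** Power is Φ(0.4/(s·√(2/90)) − 1.96), with s the square root of each variance.

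| assumed r | variance: change | variance: adjusted | ratio | power: change | power: follow-up alone | power: adjusted |
|---|---|---|---|---|---|---|
| 0 | 2.00 | 1.00 | 0.50 | 47.5% | 76.5% | 76.5% |
| 0.3 | 1.40 | 0.91 | 0.65 | 62.1% | 76.5% | 80.3% |
| 0.5 | 1.00 | 0.75 | 0.75 | 76.5% | 76.5% | 87.3% |
| 0.7 | 0.60 | 0.51 | 0.85 | 93.4% | 76.5% | 96.4% |
| 0.8 | 0.40 | 0.36 | 0.90 | 98.9% | 76.5% | 99.4% |

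With 60 per arm, as a loss scenario, power at r = 0.3 is 45.7%, 59.1% and 63.2% in the same order.

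**Step 4: linkage.** Both a patient's change and a baseline adjustment need that patient's two scores side by side. The section 5a statement on anonymity follows a broken sentence about a separate care-satisfaction survey, so it may cover only that survey or all of them. In section 5b the study code would permit linkage, while aggregate data, taken literally, would not. An unadjusted comparison of follow-up scores needs only the arm label.

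**The case against.** The strongest reply is that no analysis has been fixed. The phrase is a purpose clause in a list of assessments, and the model is commonly left to the SAP, which is not shown. A model for change with baseline as covariate gives the same treatment effect as follow-up adjusted for baseline, so the wording is compatible with the better analysis. This stands in part: a reader might infer that the protocol commits the trial to testing unadjusted change scores, and the text does not say so. But satisfaction is the only survey given a comparison, and the ordinary reading of that comparison is the weaker analysis.

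A reader might also infer that newly diagnosed patients will be surveyed before any treatment decision exists. The documents do not establish this. The Appendix 1 sentence concerns contact by the lay health worker, not the baseline survey. The appendix is headed as a different pilot, with its own stage criteria and a 5-month survey. Section 4e includes referral by the primary oncologist, so some patients will already have seen one. The survey's items are not described either. A pre-decision baseline is a possibility that the entry criteria leave open.

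Three further limits stand. The size of the loss depends on an unknown r and on equal SDs, and equal SDs are least safe if baseline rates something different. The outcome is not primary. And section 2a speaks of changes only for satisfaction, so the text gives no ground for extending the criticism to PAM or FACT-G.

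**Conclusion.** The point holds as a low-cost efficiency improvement on a non-primary outcome. Comparing follow-up scores adjusted for baseline is never less precise in large samples than comparing changes, and is usually more precise. Under equal SDs the change analysis carries the information of a fraction (1 + r)/2 of the patients: 65% at r = 0.3 and 85% at r = 0.7. Below r = 0.5 it does worse than ignoring baseline. These figures rest on an assumed r, and the power figures also on an assumed effect size, allocation ratio and complete follow-up. The documents do not allow the actual loss to be stated.

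The treatment effect is not biased under either analysis, and the primary endpoint is untouched. Before either analysis can be run, sections 2a and 5 need to agree on whether a patient's surveys are linked.

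**What to change.** In section 2a, replace the purpose clause with: *to compare satisfaction at 6 and 12 months between arms, adjusted for the score at randomization*. Add that patients with no baseline rating stay in the analysis, for example by setting the missing baseline to a constant and including a missing-baseline indicator. This is sound so long as missingness at baseline cannot depend on arm, which holds if the survey is taken before the patient learns the allocation.

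In section 5, say which surveys are anonymous. Confirm that the satisfaction with decision-making surveys are linked within patient by the study code, and that coded individual-level data are available to whoever runs the analysis. If they are not, the protocol should speak only of an unadjusted comparison of follow-up scores.

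The cost is one phrase in section 2a, a clarifying sentence or two in section 5 and a standard covariance model. No extra visits or patients are needed, and no extra data if the surveys already carry the study code.
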